9.5. Vital Signs

The vital signs data, including orthostatic systolic and diastolic blood pressure (calculated as standing value minus supine value), orthostatic heart rate, respiratory rate (recorded only supine), and body temperature, will be summarized with descriptive statistics by treatment group at baseline and at each scheduled postbaseline visit through follow-up visit. Both observed values and changes from baseline will be summarized.

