9.3.1. Vital Sign Measurements, Height, and Weight

Vital signs will be measured for the following: orthostatic systolic and diastolic blood pressure, orthostatic pulse rate, respiratory rate, and body temperature.

The same method should be used to take body temperature throughout the study. Body temperature may be measured orally or at the forehead, ear, or rectum.

Blood pressure and pulse rate will be measured using a calibrated non-invasive blood pressure cuff after the subject has been supine for at least 5 minutes and after approximately 2 minutes standing, if possible.

Vital sign measurements will be obtained before any scheduled blood sample collection at screening and then at the time points specified in the schedule of assessments (Table 8).

Height will be measured at screening only. Height and weight will be measured with subjects not wearing shoes; and weight will be measured with subjects not wearing outerwear (eg, jackets or coats).

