11.4.3. Other

11.4.4. Safety

• Safety endpoints include the occurrence of TEAEs, observed and changes from baseline in clinical laboratory tests (hematology and clinical chemistry), vital sign measurements (including orthostatic blood pressure and pulse rate), 12-lead ECG parameters, and scores from the C-SSRS.

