4.4. Safety Endpoints

- Occurrence of TEAEs
- Values and changes from baseline for clinical laboratory tests (hematology and clinical chemistry)
- Values and changes from baseline for vital sign parameters (including orthostatic blood pressure and pulse rate)
- Values and changes from baseline for 12-lead electrocardiogram (ECG) parameters
- Scores from the Columbia-Suicide Severity Rating Scale (C-SSRS)

Neurocrine Biosciences, Inc. Statistical Analysis Plan Study NBI-1065846-MDD2020 16August2023

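### SAP 9.5 names standing minus supine as its only blood pressure variable, so an equal shift in both positions would show as zero change

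*SAP*

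**What the plan says.** Protocol 9.3.1 lists the vital signs as "orthostatic systolic and diastolic blood pressure, orthostatic pulse rate, respiratory rate, and body temperature". It has blood pressure and pulse rate taken "after the subject has been supine for at least 5 minutes and after approximately 2 minutes standing", with the qualification that this is done where possible. Levels in two positions are therefore collected.

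The endpoint wording is open. SAP 4.4 has "Values and changes from baseline for vital sign parameters (including orthostatic blood pressure and pulse rate", and Protocol 11.4.4 uses nearly the same words. Neither gives a formula.

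SAP 9.5 sets out what is tabulated: the vital signs data, "including orthostatic systolic and diastolic blood pressure (calculated as standing value minus supine value), orthostatic heart rate". For blood pressure it thus names the orthostatic systolic and diastolic values and defines them in a parenthesis as the standing reading minus the supine reading. From heart rate on, the list reads "orthostatic heart rate, respiratory rate (recorded only supine), and body temperature". The section then says: "Both observed values and changes from baseline will be summarized". No supine or standing blood pressure is named there or in any other SAP section.

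SAP 9.7 separately summarises heart rate from the ECG, by treatment group and visit, as observed values and as change from baseline. Protocol 9.3.4 has those ECGs recorded after supine rest.

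**The concern.** A within-visit difference measures postural response. It carries no information on the level of blood pressure. If the drug raised or lowered pressure by a similar amount lying and standing, the planned table would show little or no change, and a reader could take that as evidence that pressure was unaffected.

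This matters because SAP 9 counts vital signs among the measures of the safety profile, and Protocol 2.2 describes the drug as potentially first-in-class with no known class effects. The multiple-dose cohorts described in Protocol 4.2 received 4 weekly doses; this trial plans 8.

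**Working it through.** The plan gives no figure for vital signs, so there is none to reproduce. Safety analysis is descriptive (SAP 9), so sample size, power and alpha do not enter. The check is algebra on the stated definition, then a comparison of sections.

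**1. Blood pressure variable.** From SAP 9.5, D = standing - supine. With change from baseline as defined in SAP 5.4:

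change in D = (shift in standing) - (shift in supine).

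The shifts below are illustrative assumptions in mmHg, not figures from the documents.

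| Supine shift | Standing shift | Change in D |
|---|---|---|
| +10 | +10 | 0 |
| -10 | -10 | 0 |
| +20 | +20 | 0 |
| +10 | +5 | -5 |
| +10 | 0 | -10 |
| 0 | -10 | -10 |

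As a single-subject example, take systolic pressure of 120 supine and 115 standing at baseline, then 140 and 135 at Day 57. D is 115 - 120 = -5 at baseline and 135 - 140 = -5 at Day 57. The change in D is 0, while each position rose by 20.

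The first three rows show that an equal shift cancels at any size and in either direction. The fourth shows that an unequal shift leaves only the difference between positions. The last two give the same result from different events: a supine rise and a standing fall.

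**2. Does another planned summary carry the level?** The sentence in SAP 9.5 promising observed values refers, on its plain reading, to the variables just listed, so it yields observed values of D. The parameters listed match those in Protocol 9.3.1, so the list reads as complete. SAP 9.5 plans no shift table, threshold count or outlier summary for blood pressure.

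**3. Missing standing readings.** Where standing was not possible, D cannot be calculated, and SAP 9 does not impute safety data. That subject's supine reading then enters no named blood pressure summary.

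**4. Heart rate.** The subtraction is attached to blood pressure only; orthostatic heart rate has no formula. Supine heart rate is available from the ECG table. In the Protocol's schedule of assessments (Table 8), post-baseline vital signs fall on Days 8, 29, 57/ET, 78 and 106, which is 5 visits. Unconditional post-baseline ECG visits are Days 29 and 57/ET, which is 2 of those 5; there is also a 2-hour postdose ECG on Day 1. Day 8 has no scheduled ECG, and Days 78 and 106 have one only if a Treatment Period ECG was abnormal.

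**The case against.** The strongest reply is that the SAP rules nothing out. Both SAP 9.5 and SAP 4.4 introduce their lists with an open word, and the remark that respiratory rate is taken only supine suggests that the authors had positions in mind. The Protocol also uses *orthostatic* as a label for readings taken lying and then standing, so the SAP may be adding a derivation to that label rather than dropping the levels. SAP 5.1 says that available study data will appear in the relevant displays. Clinically significant abnormalities are followed up and can be reported as adverse events, and Protocol 2.2 and 4.2 report no clinically significant vital sign findings in earlier studies.

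Part of this stands. A reader might infer that the SAP forbids positional summaries; it does not, it only fails to name them. But an explicit formula is what a programmer will follow, and the statement in SAP 5.1 concerns subjects with incomplete data rather than which variables to derive. Adverse event reporting depends on an investigator judging an individual case and does not show a shift in group means. The earlier findings make a large effect less likely; they do not make this table able to show one.

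A reader might also infer that a heart rate shift in both positions would vanish. The documents do not support that: no subtraction is stated for heart rate, and the supine ECG values would show such a shift at the ECG visits.

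**Conclusion.** The point holds for blood pressure. Followed as written, SAP 9.5 gives a change of 0 for any shift of equal size in both positions, whatever the sample size, and a non-zero change cannot be attributed to a position. This rests on reading the blood pressure list in SAP 9.5 as complete, which its match with Protocol 9.3.1 supports but does not prove. No document figure indicates that such a shift is expected, so the size of any real loss is unknown.

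For heart rate the gap is smaller: an undefined variable, and coverage of the supine level at fewer visits than vital signs. The gap is in the planned summaries only. Collection, the efficacy analyses and the design figures are unaffected.

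**What to change.** In SAP 9.5, state that supine and standing systolic pressure, diastolic pressure and pulse rate are each summarised, observed and as change from baseline, by visit and treatment group. Keep the standing-minus-supine difference as an additional row, and give its formula for pulse rate as well as for blood pressure.

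The cost is a few lines of SAP text and extra rows in a table already planned. No new data are needed, and the sample size and significance level do not change.

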9.6. Body Weight

The body weight data (in units of kilograms) will be summarized with descriptive statistics by treatment group at baseline and at each scheduled postbaseline visit through follow-up visit. Observed values and absolute and percent changes from baseline will be summarized.

9.7. Electrocardiogram (ECG)

The triplicate values of the quantitative ECG variables (heart rate, PR interval, QRS duration, QT interval, and corrected QT interval using Fridericia's formula [QTcF]) measured at each visit will be averaged for the purpose of analysis. For the categorical ECG interpretation variable (the investigator's assessment of the ECG as "Normal", "Abnormal, not Clinically Significant", or "Abnormal, Clinically Significant"), which is also reported in triplicate, the value that represents the greatest degree of abnormality will be used in all summary tables. If less than 3 values are recorded at an assessment, then the average/greatest abnormality of the available value(s) will be used.

The quantitative ECG variables will be summarized with descriptive statistics by treatment group at baseline and at each scheduled postbaseline visit through follow-up visit. Both observed values and changes from baseline will be summarized. Frequency counts and percentages for the ECG interpretation variable categories will be summarized at each scheduled visit.

Categorical summaries will be presented for the QTcF interval data. For these summaries, a subject's highest reported postbaseline value (including values reported at unscheduled visits) will be used to determine in which category(s) the subject will be counted. The averaged triplicate values will be used when determining each subject's highest reported values.

Two categorical summaries will be presented for the QTcF intervals. For the first summary, the number and percentage of subjects in each treatment group whose highest reported QTcF postbaseline value meets the following thresholds will be summarized:

Neurocrine Biosciences, Inc. Statistical Analysis Plan Study NBI-1065846-MDD2020 16August2023

- Greater than 450 msec
- Greater than 480 msec
- Greater than 500 msec

The second categorical summary will display the number and percentage of subjects in each treatment group whose largest QTcF increase from their baseline value meets the following thresholds:

- Greater than 30 msec
- Greater than 60 msec

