4. STUDY DESIGN

4.1. Overall Study Design

This is a Phase 2, randomized, double-blind, parallel-group, proof-of-concept study comparing use of NBI-1065846 with placebo for improvement of anhedonia in patients with MDD.

The study consists of a Screening Period of up to 28 days (Days -28 to -1), an 8-week Treatment Period (Days 1 to 57), and an 8-week Safety Follow-up Period (with visits at 4 and 8 weeks [Days 78 and 106] after last dose of study treatment).

Approximately 88 subjects are planned to be enrolled in the study. Eligible subjects include patients with MDD who have been treated with antidepressant medication(s) and who continue to have anhedonia (Snaith-Hamilton Pleasure Scale [SHAPS] ≥30 [Krystal et al., 2020; Trostheim et al., 2020]). Subjects currently receiving antidepressant medication(s) must be receiving them for ≥8 weeks prior to screening at or above the therapeutic dose based on the Massachusetts General Hospital - Antidepressant Treatment Response Questionnaire (MGH-ATRQ). Subjects not currently receiving pharmacological treatment for depression must have received ≥1 antidepressant medication(s) at a therapeutic dose per MGH-ATRQ for ≥8 weeks in the current or most recent episode of depression. To ensure adequate representation of subjects across ranges of depression severity, the Sponsor may add limits to prevent further enrollment in specific subgroups based on Hamilton Depression Rating Scale-17 Item (HAM-D17) scores at baseline.

Study treatment will be administered as monotherapy or as an adjunctive treatment to the subject's current oral antidepressant medication(s); subjects receiving antidepressant medication(s) at screening are expected to continue using them at the same dose throughout the study.

Subjects will be randomized in a 1:1 ratio in a double-blinded fashion to receive either NBI-1065846 or placebo, administered on a weekly basis, for a period of 8 weeks. The randomization will be stratified based on the Hamilton Depression Rating Scale-17 Item (HAM-D17) score at baseline: remission (HAM-D17 \leq 7), mild illness (HAM-D17 from 8 to 18), and moderate to severe illness (HAM-D17 \geq 19) (Zimmerman et al., 2013).

The end-of-study will be the last scheduled visit assessments of the last subject or last scheduled procedure shown in the schedule of assessments (Table 8) for the last subject in the study.

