9.3.4. Electrocardiogram

Triplicate 12-lead ECG will be recorded (at least 1 minute apart and within 15 minutes) after the subject has rested supine for at least 5 minutes. The ECG parameters that will be assessed include heart rate, PR interval, QRS duration, QT interval, and QTcF (machine readings or calculated). Additionally, the occurrence of de- and re-polarization, ectopic cardiac activity and rhythm disorders or other abnormalities will be assessed. Based on the review of these parameters, the investigator will note if the ECG is Normal, Abnormal not Clinically Significant, or Abnormal Clinically Significant. If the ECG is Abnormal Clinically Significant, the

investigator will provide a description of the abnormality recorded on the AE eCRF. The ECG schedule is provided in Table 8.

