Virtual Visit				X		X			
AE assessment	X	X	X	X	X	X	X	X	X
Concomitant medications	X	X	X	X	X	X	X	X	X
Schedule exit interview							X		

AE=adverse event; ; CGI-S= Clinical Global

Impression – Severity; C-SSRS=Columbia-Suicide Severity Rating Scale; DARS=Dimensional Anhedonia Rating Scale; ECG=electrocardiogram; ET=early termination; FSH=follicle-stimulating hormone; HAM-D17=Hamilton Depression Rating Scale-17; MADRS=Montgomery-Åsberg Depression Rating Scale; MGH-ATRQ=Massachusetts General Hospital - Antidepressant Treatment Response Questionnaire; MINI=Mini-International Neuropsychiatric Interview; PCRS=Placebo-Control Reminder Script;

PK=pharmacokinetics;

; SAFER= State versus Trait, Assessability, Face Validity, Ecological Validity,

Rule of Three P's; SHAPS=Snaith-Hamilton Pleasure Scale W=week

- ^a Subjects will undergo screening procedures that may be completed in 1 or more visits during the Screening Period of up to 4 weeks. Subjects may be rescreened once based on the clinical judgment of the investigator in collaboration with the sponsor or designee. The screening period may be extended by up to 14 days in extenuating circumstances in consultation with the Sponsor or designee.
- ^b Assessments on Day 1 should be performed prior to study treatment administration.
- ^c Subjects will return to the clinic approximately 4 and 8 weeks following their final dose for safety follow-up or 7 days (±2) for the ET visit assessments if the subject discontinues study treatment or withdraws consent to participate in the study.
- d After consent is obtained, the registry database check should be performed as early as possible at the screening visit to avoid unnecessary procedures.
- ^e Height will be collected at screening only.
- f Triplicate 12-lead ECGs will be performed (at least 1 minute apart and within 15 minutes) after the subject has rested supine for at least 5 minutes on screening, Day 1, Day 29, and Day 57 or ET visit. On Day 1 and Day 29, ECGs will be performed at predose and 2 hours postdose. ECGs are also needed on Day 78 and Day 106 if ECG(s) during the Treatment Period were abnormal.
- g Vital signs will be measured for the following: orthostatic systolic and diastolic blood pressure, orthostatic pulse rate, respiratory rate, and body temperature. The same method should be used to take body temperature throughout the study.

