9. SAFETY

The safety objective of the study is to characterize the safety profile of NBI-1065846 as measured by TEAEs and SAEs, vital signs, clinical laboratory tests, ECG, medications, and safety scales. All outputs for safety endpoints will be based on the Safety Analysis Set. The analysis of the safety data will be based on descriptive statistics and presented by treatment group and the study visit unless otherwise noted. Safety data will not be subject to any imputation and will be summarized on an observed case basis. No formal hypothesis-testing analysis of safety data will be performed.

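### By-arm ECG summaries run through follow-up, but follow-up ECGs are taken only after an abnormal Treatment Period ECG, so those rows are not a randomised comparison

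*SAP*

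**What the plan says.** **ECG collection.** Protocol Appendix A, Table 8, footnote f has triplicate ECGs taken after the subject has "rested supine for at least 5 minutes on screening, Day 1, Day 29, and Day 57 or ET visit". It adds: "On Day 1 and Day 29, ECGs will be performed at predose and 2 hours postdose". For follow-up it says: "ECGs are also needed on Day 78 and Day 106 if ECG(s) during the Treatment Period were abnormal". The ECG line of Table 8 has no mark in either follow-up column.

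**The trigger.** Protocol section 4.1 describes "an 8-week Treatment Period (Days 1 to 57"), so the predose Day 1 ECG lies inside the period that can trigger follow-up. Under protocol section 9.3.4, "the investigator will note if the ECG is Normal, Abnormal not Clinically Significant, or Abnormal Clinically Significant". Two of these three categories are abnormal, and footnote f does not say whether both count.

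**ECG summary.** SAP section 9.7 says: "The quantitative ECG variables will be summarized with descriptive statistics by treatment group at baseline and at each scheduled postbaseline visit through follow-up visit". It covers observed values and changes from baseline. The investigator's interpretation is tabulated at each scheduled visit. Neither statement mentions conditional collection.

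**Missing values.** SAP section 9 says: "Safety data will not be subject to any imputation and will be summarized on an observed case basis".

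**Visit windows.** SAP Table 2 (safety) sets the Day 57 row at Day 51 to the last dose day, the Day 78 row at last dose +1 to last dose +42, and the Day 106 row at last dose +43 onward. Protocol section 6.2 puts the last scheduled dose on Day 50.

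**The concern.** An observed-case table of follow-up ECGs shows only subjects who had an abnormal ECG earlier. Whether a subject qualifies depends on what happened after randomisation, and a drug that alters the ECG changes who qualifies. If it lengthens QTcF, active subjects with ordinary underlying values can be drawn in, while placebo subjects qualify only with long underlying values or some other abnormality. The two groups then differ for reasons unrelated to any drug effect still present at follow-up.

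Follow-up rows are where a reader looks to see whether an ECG change persisted or resolved. Here the difference between arms mixes the residual effect with the selection, and the table gives no sign of it.

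SAP sections 9.5 and 9.6 describe vital signs and body weight as running through follow-up in the same way. That suits them, because Table 8 schedules both for everyone at Days 78 and 106. It does not suit the ECG.

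**Working it through.** The documents give no mean, SD or expected effect for any ECG variable, so there is no plan figure to reproduce. The selection follows from the text alone. The sizes below rest on assumed values.

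**1. Where the bias comes from.** Let u be a subject's underlying QTcF, r the drug effect remaining at follow-up, and S = 1 if a Treatment Period ECG was abnormal. For an effect common to all subjects, the expected difference in observed follow-up means (active minus placebo) is

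r + { E[u | S = 1, active] - E[u | S = 1, placebo] }.

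The bracket is zero when everyone is measured. Change from baseline removes u and leaves r plus a smaller term from baseline measurement noise.

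**2. Assumption set A** (400,000 simulated subjects per arm): mean 410, between-subject SD 15, within-subject SD 8 msec; entry at or below 450; trigger is any of three on-treatment values above 440; drug effect +10 msec on treatment.

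- QTcF is the only trigger: 7% of placebo and 20% of active subjects are selected. Of 44 per arm, 0.07 × 44 ≈ 3 and 0.20 × 44 ≈ 9.
- r = 0: 428.4 - 434.7 = -6.3 msec observed (truth 0). Change from baseline: -0.6.
- r = 5: 433.4 - 434.7 = -1.3 msec observed (truth +5). Change from baseline: +4.4.
- If 10% or 30% of subjects also have some other ECG abnormality, the observed difference is about +2.5 (truth 0) or about +7.5 (truth +5). The bias changes sign.
- If interpretation is tabulated at follow-up, abnormal meaning above 440 and r = 0, the QTcF-only trigger gives 31% placebo against 15% active. Among all subjects it would be 3% in each arm.

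**3. Assumption set B**: mean 410, SDs 16 and 9, entry cap 460, trigger above 450, predose Day 1 ECG counted, drug effect +10 msec.

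| Other abnormality | With follow-up ECG, of 44 (placebo, active) | Observed diff, truth 0 | Change diff, truth 0 | Observed diff, truth +5 | Change diff, truth +5 |
|---|---|---|---|---|---|
| 0% | 1, 4 | -5.6 | +2.3 | -0.5 | +7.3 |
| 10% | 6, 8 | +4.5 | +0.5 | +9.4 | +5.4 |
| 30% | 14, 16 | +2.2 | +0.1 | +7.2 | +5.2 |

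The Day 29 row returns the assumed 10.0 msec throughout. Without the predose ECG in the trigger, the +7.3 becomes +4.0. If the effect sits in a quarter of subjects, persists fully and averages 10 msec, with 10% other abnormality, the change difference is +25.8.

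**4. Noise.** The SD of a change is √2 × 9 = 12.7 msec. With the unrounded counts of 5.5 and 7.5 subjects, SE = 12.7 × √(1/5.5 + 1/7.5) ≈ 7.1, so a true +5 appears negative about 24% of the time. With 44 per arm the SE is 2.7 and the chance 3%.

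**5. The windows.** With the last dose on Day 50, a Day 57 ECG falls on last dose + 7. That is after the Day 57 window closes and inside the Day 78 window (+1 to +42). Using the ±2-day allowances, the last dose falls on Days 48 to 52 and the visit on Days 55 to 59, a gap of 3 to 11 days, so the result is the same. Table 2 keeps the value nearest last dose + 28. A subject with normal ECGs then contributes the Day 57 value (21 days off target), and a triggered subject contributes the Day 78 value. The Day 78 row mixes the two. In set B with nothing persisting, and the full effect assumed still present on Day 57, that row shows +6.3 to +9.0 msec when the true Day 78 difference is 0. Only the Day 106 row is purely selected.

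**The case against.** A reader might infer that the plan hides or reverses a QTcF effect of the drug. The documents do not support that.

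- Day 1 postdose and Day 29 ECGs are scheduled for everyone, so an on-treatment effect would show there.
- Section 9.7 also reports change from baseline, which was not reversed in expectation in any scenario run.
- The direction of the observed-value bias depends on the trigger. Footnote f says only abnormal, and section 9.3.4 covers rhythm, conduction and repolarisation as well as QTcF. With other abnormalities present, the drug looks worse, not better.
- The highest-value and largest-increase QTcF tables still cover everyone with a postbaseline ECG.
- Safety is descriptive, with no hypothesis tests, and SAP section 5.1 includes n, so the small denominators would be visible.

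All of this stands and limits the weight of the point.

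Two textual defences are weaker. The first is that Table 2's follow-up rows exist for laboratory tests and vital signs, and that the interpretation sentence covers scheduled visits only. That is fair for Table 2 and the interpretation table, but the sentence on quantitative variables expressly extends to follow-up. The second is that visible n is enough. It shows that few subjects contribute, but not that they were chosen by outcome. One practical objection also holds: dropping the Day 78 row without correcting Table 2 would discard the Day 57 ECGs collected from everyone.

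**Conclusion.** The point holds as a descriptive safety-reporting flaw that is worth correcting because the correction is cheap. Footnote f and SAP section 9.7 together produce by-arm follow-up rows whose membership depends on a post-randomisation outcome, so the differences between arms in those rows are not randomised comparisons. Observed-value differences can be masked, reversed or exaggerated. Change from baseline stays much closer to the truth when the effect is similar across subjects, and can be badly inflated when it is concentrated in a few.

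The selection and the window conflict follow from the documents. The msec figures do not: they depend on assumed QTcF means, SDs, triggers and effects, and show only that the sign of the bias cannot be known in advance. No efficacy analysis or on-treatment ECG row is affected. A smaller related point is that the highest-postbaseline QTcF categories have no stated end date, so triggered subjects get extra chances to cross a threshold.

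**What to change.** 1. In SAP section 9.7, end the by-arm ECG summaries, quantitative and interpretation, at the Day 57/ET visit.
2. In the same revision, correct SAP Table 2, or use the nominal visit for ECGs, so that Day 57 ECGs fall in the Day 57 row. Step 1 should not be made without this.
3. Report Day 78 and Day 106 ECGs in a subject listing with baseline, worst on-treatment and follow-up values. Alternatively, use a separate table that shows n per arm and is labelled as triggered by an abnormal ECG.
4. Label any follow-up values used in the highest-postbaseline QTcF categories as conditionally collected.
5. Have the sponsor state which of the section 9.3.4 categories footnote f means by abnormal, and whether the predose Day 1 ECG counts, so that readers can see how subjects entered the listing.

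The cost is SAP wording and a short clarification of footnote f. No procedure is added and no data are lost. The downside is that two sparse table rows become a listing.
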